15.4 Additional analyses to optimize dynamic prevention and treatment

For each trial, we will assess the fidelity to intervention implementation, intervention adoption, and process outcomes. We will also examine feasibility and prevention coverage in the youth multisectoral intervention pilot studies.

To understand effect heterogeneity, we will repeat the analyses outlined above within the following pre-specified subgroups: country, sex (for trials enrolling both sexes), age group (for trials enrolling adults of all ages), and may include mobility (for trials enrolling both mobile and non-mobile adults).

For each of the trials, we will provide descriptive statistics of populations and outcomes, overall as well as stratified by intervention arm and country. We will further evaluate predictors of sub-optimal outcomes using TMLE (primary) and with univariate associations (secondary). For interventions with suggested efficacy, we may examine pathways of intervention action using formal mediation analyses.^{109, 110} These analyses will be complemented with participant and provider qualitative data and mixed method approaches.

Finally, to quantify the potential spillover between randomized arms and to understand secular trends in the clinic-based intervention trials for Dynamic Prevention (outpatient department and antenatal/family planning clinic) and for Dynamic Treatment (mobile populations and heavy drinkers), we may conduct retrospective record review to obtain endpoint measures before the trials' initiation and compare them with endpoints measured during the trials' follow-up through a pre-post analysis. Additionally, we may use difference-in-differences to compare each trial's intervention arm and each trial's control arm to the external controls.¹¹¹

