9.2.3. Phase A Optimization

The results of phase A will be used to finalize Dynamic Treatment and Dynamic Prevention packages for evaluation in Phase B via the following steps: 1) evaluation of short term (48 week) effects on primary and secondary outcomes to eliminate setting and subpopulation components unlikely to contribute substantially to population-level effects; 2) evaluation of implementation outcomes and, 3) structured stakeholder consultation, in which the above data are reviewed, together with a systematic review of external data on concurrent advances in HIV treatment and prevention. With the many new prevention modalities in development, we expect that some of those may be integrated into phase B study design.

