For all endpoints, we will test the **null hypothesis** of no improvements in outcomes due to the intervention with a one-sided test at the 5% significance level. We will also report point estimates and 95% confidence intervals for each effect measure and the arm-specific average outcomes. Standard error estimation will be with the estimated influence curve, and statistical inference will follow from the Central Limit Theorem (i.e., using the standard normal distribution).⁴

For all endpoints, we will also examine the intervention effect within **subgroups** defined by sex, age group (<60 years vs. ≥ 60 years), country, site, baseline HTN severity, and HIV status. In subgroups with fewer than 41 participants, we will limit the candidate estimation approaches to main terms adjustment for a single covariate or the simple mean.

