We will test the **null hypothesis** that the intervention did not improve viral suppression at week-48 using a one-sided test at the 5% significance level. We will also report point estimates and 95% confidence intervals for each effect measure and the arm-specific outcomes at baseline and week-48. Standard error estimation will be based on the estimated influence curve, and statistical inference will follow from the Central Limit Theorem (i.e., using the standard normal distribution).¹

Secondary analyses: To assess the robustness of these findings, we will repeat these analyses using the unadjusted effect estimator. We will also repeat these analyses excluding persons with missing endpoints and using TMLE to adjust for missing endpoints.

Subgroup analyses: We will repeat these analyses within strata defined by country, sex, age group, mobility level, alcohol use, baseline viral suppression status, and trial enrollment criteria. In subgroups analyses, we will limit the candidate estimation approaches to main terms adjustment for a single covariate or the simple mean and use leave-one-out cross-validation for subgroups with <40 participants. To further understand effect heterogeneity, we may conduct variable importance measures (unadjusted and adjusted) to understand baseline predictors of endline viremia, overall and by arm.

Secondary endpoints compared by arm: We will implement analogous analyses to evaluate the intervention effect on retention in care and ART possession.

5. Intervention Implementation

Within the intervention arm, we will describe coverage and uptake of the intervention at baseline (week-0), week-12, week-24, and week-36 study visits:

- Visit coverage: number and proportion who attended study visits
- Choice of intervention components: number and proportion* who selected the travel pack, longer ART refills, off-site refills, and/or facilitated out-transfer
- Stocking and re-stocking of travel pack components: number and proportion* who selected the hotline, emergency ART, the travel checklist, and/or discrete ART packaging
- Choice of visit type: number and proportion who had visits in-person at the clinic, in-person in the community, or virtually on the mobile hotline

[figure not shown]

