The intervention is culturally-adapted and skills-based alcohol counseling, consisting of in-person sessions at baseline and every 12 weeks as well as phone-based “booster” calls every 3 weeks between in-person sessions. The intervention is delivered by lay counselors trained by a licensed clinical psychologist, who also provides ongoing supervision and feedback.

The primary objective is to evaluate if the intervention improved viral suppression (<400 copies/mL) among PWH with unhealthy alcohol use after 24 weeks of follow-up. Secondary endpoints, compared between randomized arms at 24-weeks, include alcohol use, as measured by Alcohol Use Disorders Identification Test—

Consumption [AUDIT-C] or phosphatidylethanol [PEth]. Additionally, within the intervention arm, we will report completion of counseling sessions and their fidelity.

2. Population and Characteristics

The population of interest is PWH who are

- Aged 18+ years
- Enrolled or new to HIV care
- At risk of viral non-suppression:
 - HIV RNA>400 copies/mL in the past 12 months
 - Missed visit (>2 weeks and <90 days from scheduled appointment) in the past 6 months
 - Re-engaging in care (>90 days from last scheduled visit) in the past 6 months
 - New HIV diagnosis (not yet on ART or started ART within past 1 month)
- Have unhealthy alcohol use: AUDIT-C over the past 3-months of ≥ 3 for women or ≥ 4 for men

To characterize measurement of this population, we will provide a participant flow diagram (i.e., a CONSORT diagram). Overall and stratified by trial arm and further by sex, we will summarize the baseline characteristics, including sex, age, country, marital status, occupation, education level, literacy level, trial recruitment site (i.e., venue-based or clinic), trial enrollment criteria, baseline ART status and regimen, baseline viral suppression status, and baseline alcohol use via AUDIT-C score and PEth levels. We will categorize age as “younger” if aged 18-30 years. When treated continuously, PEth will be log-10 transformed and values below the limit of quantification (8 ng/mL) set to 0.

3. Endpoint Measurement and Definition

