Primary effect estimates will be for the study sample and on the **ratio scale**:

$1/n \sum_{i=1}^n Y_i(1) \div 1/n \sum_{i=1}^n Y_i(0)$, where $Y_i(1)$ denotes the counterfactual outcome for participant i under the intervention and $Y_i(0)$ denotes the counterfactual outcome for participant i under the control.^{9–11} Secondary comparisons will be on the difference scale.

We will test the **null hypothesis** that the intervention did not improve viral suppression at 24-weeks using a one-sided test at the 5% significance level. We will also report point estimates and 95% confidence intervals for each effect measure and the arm-specific outcomes at baseline and 24-weeks. Standard error estimation will be based on the estimated influence curve, and statistical inference will follow from the Central Limit Theorem (i.e., using the standard normal distribution).¹

Secondary analyses: To assess the robustness of these findings, we will repeat these analyses using the unadjusted effect estimator. We will also repeat these analyses including persons who moved out of the study region, excluding persons with missing endpoints, and using TMLE to adjust for missing endpoints.

Subgroup analyses: We will repeat these analyses within strata defined by country, sex, age group, trial recruitment site, trial enrollment criteria, baseline viral suppression status, and baseline alcohol use: AUDIT-C score 3-5/women or 4-5/men, AUDIT-C score 6-7, AUDIT-C score 8+, PEth<8 ng/mL (undetectable), PEth≥8 ng/mL, PEth<50 ng/mL, PEth≥50 ng/mL, PEth≤200 ng/mL, Peth>200 ng/mL. In subgroups analyses, we will limit the candidate estimation approaches to main terms adjustment for a single covariate or the simple mean and use leave-one-out cross-validation for subgroups with <40 participants. To further understand effect heterogeneity, we may conduct variable importance measures (unadjusted and adjusted) to understand baseline predictors of endline viremia, overall and by arm.

Secondary endpoints compared by arm: We will implement analogous analyses to evaluate the intervention effect on alcohol use. In these analyses, the primary approach will exclude persons with missing measures of alcohol use at 24-weeks. We will again examine the robustness of this approach (i.e., adjust with TMLE for missing measures and include persons who moved out of the study region). When examining the effect on log-10 PEth values, we will use the difference scale.

5. Intervention Fidelity and Implementation

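### Phase A subgroup analyses repeat the 5% test inside each stratum and never compare effects between strata, so they cannot answer the heterogeneity question they are set

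*Protocol*

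**What the plan says.** Protocol 15.4 gives both the aim and the method for every Phase A trial: "To understand effect heterogeneity, we will repeat the analyses outlined above within the following pre-specified subgroups". The firm factors are country, sex and age group, with mobility optional. The analyses being repeated carry a 5% test, point estimates and 95% CIs (Protocol 15.2 and 15.3).

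The SAPs extend the lists:

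- **Alcohol SAP, section 4:** "We will repeat these analyses within strata defined by country, sex, age group, trial recruitment site, trial enrollment criteria, baseline viral suppression status", then three AUDIT-C bands ("AUDIT-C score 3-5/women or 4-5/men, AUDIT-C score 6-7, AUDIT-C score 8" and above) and three overlapping PEth cuts, running from undetectable through "PEth≥8 ng/mL, PEth<50 ng/mL, PEth≥50 ng/mL, PEth≤200 ng/mL, Peth>200 ng/mL".
- **Mobility SAP, section 4:** "We will repeat these analyses within strata defined by country, sex, age group, mobility level, alcohol use, baseline viral suppression status", plus enrollment criteria.
- **Hypertension linkage and severe hypertension SAPs, 2.1:** "For all endpoints, we will also examine the intervention effect within" subgroups. The linkage SAP (2.2) adds that subgroup analyses are run in the same way as the primary one.
- **Outpatient, antenatal and village prevention SAPs, section 4:** the same approach with five factors each.

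No document plans an interaction test, a between-stratum contrast, multiplicity control for subgroups, an exploratory label or a reading rule. The only formal contrast of two effects (linkage SAP 2.3, Delta Method) compares two endpoints, not two subgroups. Predictor analyses are firm in Protocol 15.4 and linkage SAP 2.6, and optional in the other SAPs.

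**The concern.** The aim is to learn whether the effect differs between groups. The method asks, group by group, whether the effect differs from zero. Each stratum has a fraction of the trial's sample, so its power is well below the design power, and some strata will miss significance even when the true effect is identical everywhere. A reader who then sees significance in women but not men, or at one PEth cut but not another, is invited to conclude that the intervention works only for some.

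The predictor analyses do not fill the gap. They identify who has poor outcomes. Running them by arm still gives no estimate of a difference in treatment effect with a standard error.

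At stake is the interpretation of the Phase A subgroup tables. No primary estimate, primary error rate or sample size is affected.

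**Working it through.** **1. The plan's own figure.** Alcohol trial (Protocol 15.2.1, Alcohol SAP appendix): 200 per arm, 40% versus 54%, two-sided 5%. The two-proportion formula is

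power = Φ{[√n·d − z·√(2p̄(1−p̄))] / √(p0(1−p0)+p1(1−p1))}

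with d = 0.14 and p̄ = 0.47, so the two root terms are 0.706 and 0.699. This gives (1.980 − 1.96×0.706)/0.699 = 0.85 and power 80.3%, matching the stated 80%. With the planned one-sided test (z = 1.645), power is 87.9%.

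**2. Power inside a stratum, one-sided 5%, same effect:** 79% at 150 per arm, 63% at 100, 40% at 50 and 22% at 20.

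**3. One two-level factor, uniform effect.** Chance that exactly one stratum is significant:

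- 50:50 split: 2 × 0.634 × 0.366 = 46%.
- 75:25 split: 0.786 × 0.597 + 0.403 × 0.214 = 56%.

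**4. Stratum counts.**

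- Alcohol: country 2, sex 2, age 2, recruitment site 2, enrollment criteria 4, baseline suppression 2, AUDIT-C 3, PEth 6 = 23, over 10 factors with the PEth cuts counted separately. The fourth enrollment criterion is "New HIV diagnosis (not yet on ART or started ART within past 1 month"). With the three criteria in Protocol 7.3.1 the count is 22.
- Mobility 14, linkage 13, severe hypertension 11, outpatient and antenatal 10 each.

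**5. All strata together, uniform effect at the design value.** Stratum shares are not in the documents. They were taken as even, or skewed (mostly 70:30). The test is the unadjusted difference at each SAP's 5% level and sidedness. There were 4,000 simulated alcohol trials of 400 people and 6,000 of each other trial.

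| Trial | Some strata significant, some not |
|---|---|
| Alcohol, 23 strata | 97.5–98.5% |
| Linkage, 13 | 90–94% |
| Severe hypertension, 11 | 91–92% |
| Mobility, 14 | 83–93% |
| Outpatient/antenatal, 10 | 84–88% |
| Three firm factors of 15.4, alcohol inputs, 6 | 71–76% |

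In the alcohol trial about 13 of 23 strata are significant on average, and 5.5–5.7 of 10 factors are split. The village trial was not simulated.

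**6. Sensitivity, alcohol, 23 strata.** Uniform effect of +7 points: 85%. +20: 90–97%. +25: 68–90%. +30: 38–73%. A 70% control rate with +10 points: 96–97%.

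**7. No effect at all.** At least one alcohol stratum is significant in about 44% of trials. Independent strata would give 1 − 0.95²³ = 69%, but these overlap.

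**8. Between-stratum contrasts instead.** One heterogeneity test per factor (Cochran's Q across its strata) gives a false signal about 5% of the time. Across ten uncorrected tests at least one false signal appears in 40–43% of trials (independent tests: 1 − 0.95¹⁰ = 40%). With Bonferroni this is about 6–7%.

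**9. Precision of a contrast.** For a 50:50 factor each half has SE √(0.4884/100) = 7.0 points, so the contrast has SE 9.9 points and a 95% CI of about ±19 points. Power to detect a 14-point difference in effect is about Φ(1.42 − 1.96) = 29%.

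**The case against.** The plan reports subgroup estimates with 95% CIs, and nowhere says that a mixed pattern of significance will be read as heterogeneity. The analyses sit under additional analyses or after the primary and secondary ones, in trials with one named primary endpoint. This stands: the risk is one of interpretation. It does not supply the missing contrast, and 15.4 itself names heterogeneity as the purpose.

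A reader might infer that Section 9.2.3 will drop strata on their p-values, since it uses Phase A results "to eliminate setting and subpopulation components unlikely to contribute substantially to population-level effects". The documents do not support that. Protocol 15.1 speaks of settings and subpopulations when describing whole trials: four delivery settings, and mobile persons and heavy drinkers. The 9.2.3 criterion is contribution to population-level effects, weighed with implementation outcomes, stakeholder consultation and external data. The Phase B entries for prevention and severe hypertension (7.3.2, Table 12) are not restricted by Phase A strata such as sex, country or PEth.

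A reader might also take the 98% as general. It belongs to the alcohol trial's long list at its design effect.

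The simulation assumes stratum shares, equal control rates across strata and exclusive enrollment criteria, which the SAP does not state. It uses an unadjusted difference where the alcohol, mobility and linkage SAPs use TMLE on a ratio scale. These limits affect the exact percentages, not the direction.

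Interaction tests are not free of error either: ten uncorrected ones mislead in 40–43% of trials. That is accepted, and the remedy must include a limit.

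**Conclusion.** The concern holds. The stated method cannot establish whether effects differ, and no document adds one that can. Under a uniform effect at the design value a mixed pattern is close to certain in the alcohol trial (about 98%) and very likely in the other individually randomized trials (roughly 83–94%). It is still more likely than not for 15.4's three firm factors with alcohol inputs (71–76%). These figures rest on assumed stratum shares and an unadjusted estimator, and they fall when the true effect is well above the design value.

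The change should be made because the better method is nearly free. The primary conclusions do not depend on it, and the point does not extend to the choice of Phase B components.

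**What to change.** In Protocol 15.4 and each SAP's subgroup paragraph:

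1. For each subgroup variable, report stratum estimates with 95% CIs and one between-stratum contrast on the trial's pre-specified scale: a ratio of risk ratios or a difference of differences by the Delta Method, as linkage SAP 2.3 already does for two endpoints. Use a joint test for factors with three or more levels. In the village trial, aggregate the influence curve of the contrast to the village level, because sex and age strata share villages.
2. Drop the within-stratum significance tests.
3. Label all subgroup analyses exploratory. Either name a short list of key modifiers or adjust the contrasts for multiplicity.
4. In the alcohol SAP, use one PEth cut or continuous PEth in place of the three overlapping cuts.
5. State that the predictor analyses describe outcome risk, not effect modification.

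The cost is SAP wording and a few lines of code using influence curves already computed. The downside is low power: most contrasts will be inconclusive and should be reported as such.

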15.5 Community randomized trial in Phase B

In Phase B, we will randomize the $N=16$ study communities pair-matched on predictors of the primary endpoint (HIV incidence) and stratified by country.

We will assess population-level effects with Two-Stage TMLE, an approach appropriate for cluster randomized trials.^{5, 106} In Stage I, we estimate the outcome for each community. Then in Stage II, we use a cluster-level TMLE to estimate intervention effectiveness by comparing the community-specific endpoints between randomized arms. Given the limited number of clusters, we will use Adaptive Pre-specification to optimally adjust for covariate imbalance between randomized arms, while preserving Type-I error control.¹⁰⁸ In secondary analyses, we will implement the unadjusted estimator as the contrast of the arm-specific mean outcomes. For each endpoint, we will test the **null hypothesis** of *no improvement* from the intervention with a one-sided test at the 5% significance level. We will also report point estimates and two-sided 95% confidence intervals for each effect measure and the arm-specific mean outcomes.

The **primary study outcome** is HIV incidence among adult community members and assessed at month 30 with a recency assay. Stage I estimates of HIV incidence (per 100 person-years) will account for assay characteristics, such as mean duration of recent infection (MDRI) and false recent rate (FRR). Stage II estimates will use leave-one-out cross-validation to select from the following community-level covariates the combination that maximizes empirical efficiency: baseline HIV prevalence, baseline proportion with HIV who are suppressing viral suppression (<400 c/mL), or nothing (unadjusted).

The following secondary outcomes will be compared between arms using the analogous two-stage approach:

- **Biomedical prevention coverage:** proportion of HIV-negative follow-up time during which the participant was protected from HIV by PrEP or PEP (inclusive of CAB-LA)
- **Population-level viral suppression:** proportion of adults with HIV who are suppressing viral suppression (HIV RNA level < 400 c/mL) at month 30
- **Mortality:** the incidence (per 100 person-years) of death to illness and incidence of death due to all causes among adults
- **Annual incidence of active TB disease:** overall and stratified by age group and HIV-association
- **Hypertension control** (BP<140/90 mmHg) among community members aged 30+ years at month 30
- **Prevalence of heavy alcohol use** (AUDIT-C value of 3+ among women and 4+ among men) among persons with HIV and age 18+ years at month 30
- **Infant HIV-free survival:** the proportion of infants born to women with HIV or HIV-unknown status who are alive and without HIV at month 30
- **Pediatric immunization coverage:** the proportion of children (aged < 5 years) with up-to-date vaccination at month 30

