6. STUDY DESIGN

In the “optimization” Phase A, the study will conduct randomized trials and pilot studies to assess effectiveness, fidelity and cost and improve context-specific “fit” of prevention and treatment interventions. Combining effectiveness with implementation, costing and modelling outcomes, the study will optimize intervention packages with context-specific adaptations in structured consultation with stakeholders. In the “evaluation” Phase B, the study will evaluate the effects of Dynamic Prevention and Dynamic Treatment intervention packages based on data from Phase A and new advances from outside the study, alone and in combination, on HIV incidence, biomedical prevention coverage and other health outcomes, in a pair-matched community randomized design.

*Pilot single arm study of dynamic prevention in settings of youth clubs, boda-boda drivers

We will evaluate population-level intervention implementation outcomes guided by the RE-AIM framework,⁶⁹ elucidate mechanisms of action and component intervention effects using mixed methods and multi-level mediation analyses, and estimate incremental costs and gains using micro-costing and time-and-motion studies. Finally, the study will use the HIV Synthesis Model to model outcomes and costs of Phase B results over a period of decades to inform policy and stakeholder decisions to adopt successful strategies to achieve and sustain HIV epidemic control.

Structured stakeholder consultations are formally incorporated in the study design and leverage regular and ongoing collaborations the study team has with the HIV, non-communicable disease and general health leads in Kenya and Uganda Ministries of Health and PEPFAR implementing partners at the national and the regional level.

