9.1.2. Phase B Community Randomization

The study will randomize the 16 communities (8 Ugandan and 8 Kenyan) as detailed in the Study Schema. Randomization will be stratified by country. The communities selected for randomization will not include health facilities that took part in Phase A activities.

We will utilize an established randomization strategy that is both scientifically valid and transparent to the community stakeholders and uses local idioms to make the concept of randomization easily understood by traditional leaders and community members,⁹⁶ as conducted in the SEARCH trial.⁵ Community randomization will be conceptualized as an ongoing part of the community preparedness process in partnership with the community leaders and community individuals.

For the random assignment of each community, we will employ a public lottery to achieve maximum public acceptance of the randomization results by enhancing transparency and spreading ownership of the process. For each country separately, the randomization allocation will be written on separate pieces of paper or card and folded in half to obscure the label from view. The number of cards for each level will correspond with the randomization probabilities. These cards will then be placed in a sealed box with a hand hole cut out of the top of the box. For each country separately, a computer will randomly designate ordering of community sites. Then the lottery will be conducted as a series of draws according to the computer-generated ordering. The leader with the last draw will be responsible for holding and shaking the selection box. After the drawing is complete, the host country leader will announce the interventions corresponding to each allocation. The lottery will be a public event with members of the Community Advisory Board and local leadership present along with guests from other community-based organizations and the general public to witness the lottery conducted by local chiefs or leaders. This process assures equal chance of being randomized to each level of the intervention and eliminates any residual fears of bias or rigging.

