We will assess the Dynamic Choice Prevention intervention effect with targeted minimum loss-based estimation (TMLE), which improves precision and power by adaptively adjusting for baseline outcome predictors.^{1–5} Here, we will use **TMLE with Adaptive Pre-specification** to flexibly control for baseline covariates, while maintaining Type-I error control and accounting for clustering.^{6–8} Using leave-one-village-out cross-validation, we will chose the optimal approach for estimating the outcome regression (i.e., the expected outcome given the randomization arm and adjustment covariates) and the known propensity score (i.e., the conditional probability of being randomized to the intervention given the adjustment covariates). Specifically, we will select the combination of estimators (adjustment variables + approach) that minimizes the cross-validated variance estimate, which again accounts for clustering.

Our pre-specified, candidate adjustment variables consist of sex, age, country, use of PrEP/PEP in the 6 months prior to enrollment, and nothing (i.e., unadjusted). Our pre-specified, candidate learners consist of generalized linear models (GLMs) adjusting for a single variable (beyond the intervention indicator), stepwise regression, multivariate adaptive regression splines (MARS), and the arm-specific mean outcome.

Primary effect estimates will be for the study sample and on the **difference scale**:

$1/n \sum_{i=1}^n [Y_i(1) - Y_i(0)]$, where n denotes the total participants, $Y_i(1)$ denotes the counterfactual outcome for participant i under the intervention and $Y_i(0)$ denotes the counterfactual outcome for participant i under the control.^{9–11} In other words, we will estimate an individual-level effect (i.e., weight the n individuals equally); secondary analyses will estimate a cluster-level effect (i.e., weight the J villages equally regardless of their size).^{12–14} Secondary comparisons will be on the ratio scale. All analyses will break the matches used for randomization.¹⁵

We will test the **null hypothesis** that the intervention did not change biomedical covered time with a two-sided test at the 5% significance level. We will also report point estimates and 95% confidence intervals for each effect measure and the arm-specific outcomes. Standard error estimation will be based on the estimated influence curve, appropriately aggregated to the cluster-level.^{14,16,17} Statistical inference will follow from

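### Phase B randomisation is stratified by country, but country is not a Stage II adjustment candidate; unless within-country pairs are kept or a selected covariate tracks country, the HIV-incidence test is conservative and loses power

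*Protocol*

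**What the plan says.** **Randomisation.** Protocol 9.1.2: "The study will randomize the 16 communities (8 Ugandan and 8 Kenyan"); "Randomization will be stratified by country". It then describes a public lottery run separately in each country, with communities drawing in a computer-generated order. It mentions no pairs. Section 6 instead places Phase B "in a pair-matched community randomized design", and 15.5 has the communities "pair-matched on predictors of the primary endpoint (HIV incidence) and stratified by country".

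**Analysis.** Section 15.5 uses a two-stage TMLE. Stage I estimates each community's incidence. Stage II compares arms at community level "with a one-sided test at the 5% significance level". For the primary outcome, leave-one-out cross-validation is used "to select from the following community-level covariates the combination that maximizes empirical efficiency: baseline HIV prevalence, baseline proportion with HIV"; the list in full is "baseline HIV prevalence, baseline proportion with HIV who are suppressing viral suppression (<400 c/mL), or nothing (unadjusted"). Secondary outcomes use an analogous two-stage approach, with no covariates listed. Section 15.5 does not say whether Stage II keeps or breaks the pairs.

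**Baseline data.** Protocol 9.5 has the study take no measurements in control communities before the endline survey. Community-level baseline data may be taken from existing Ministry of Health records.

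**Practice elsewhere in the programme.** Protocol 15.2 says the individually randomised Phase A analyses adjust for stratification factors. Six of the seven Phase A SAPs list country as a candidate. The hypertension linkage SAP lists site. The SAP for the village health team (VHT) cluster trial, also with 16 clusters, reads: "Our pre-specified, candidate adjustment variables consist of sex, age, country, use of PrEP/PEP in the 6 months prior to enrollment, and nothing". It also states that its analyses break the matches.

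**The concern.** Stratifying by country balances it across arms, so the true sampling variance of the arm contrast contains no between-country component. An unpaired variance estimate without a country term still counts the Kenya–Uganda difference as noise within each arm. The standard error is then larger than the actual variability of the estimate.

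This would happen under two conditions. First, the pairs are broken, or were never formed, as 9.1.2 reads. Second, no selected covariate stands in for country. The second is plausible because both listed covariates depend on ministry records in the eight control communities and may be missing there or measured differently from the intervention arm. Country is known for all 16 communities at no cost. At stake is power for the primary endpoint in a trial with only 16 units.

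**Working it through.** **Inputs from Protocol 15.5.** Eight communities per arm, 5,000 adults each, 90% tested, 10% HIV prevalence, incidence 0.5 vs 0.3 per 100 person-years (PY), MDRI 238 (taken as days), FRR 0%, design effect 1.3, two-sided 5%, power 80%.

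**1. Reproduce the plan's power.**
- Tested per arm: 8 × 5,000 × 0.9 = 36,000, of whom 3,600 are HIV-positive and 32,400 HIV-negative.
- Expected recent infections: 32,400 × 0.005 × 238/365.25 = 105.6 in control; at 0.003, 63.3.
- Relative variance of an arm's incidence, with R recent infections and H positives: 1.3 × [(1 − R/H)/R + 1/(0.9H)]. This gives 0.0124 (control) and 0.0206 (intervention).
- SE of the difference: √(0.5² × 0.0124 + 0.3² × 0.0206) = 0.070.
- Power: Φ(0.2/0.0703 − 1.96) = 0.81; 0.80 on the log scale. The stated 80% reproduces. The one-sided equivalent is about 0.88.

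**2. Between-community variation implied by 1.3.** A control community yields 105.6/8 = 13.2 recent infections, so the relative sampling variance is 1/13.2 = 0.076. The design effect adds 0.3 × 0.076 = 0.023, a coefficient of variation of 0.15.

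**3. Size of a country difference.** For incidence ratio r with the overall mean fixed, the relative between-country variance is b = ((r − 1)/(r + 1))². The documents give no r, so a range is shown.

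| r (assumed) | b | Design effect if added to 1.3: 1.3 + 13.2b |
|---|---|---|
| 1.25 | 0.012 | 1.46 |
| 1.35 | 0.022 | 1.59 |
| 1.5 | 0.040 | 1.83 |
| 2.0 | 0.111 | 2.77 |

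A ratio of about 1.35 would use up all the between-community variance that 1.3 allows.

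**4. Simulated one-sided 5% power at a 40% reduction.** Recent infections are Poisson with between-community variation, four communities per country and arm, 20,000 to 40,000 runs per setting. The unpaired test without country uses 14 df; the test with country uses 13.

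| r | 1.3 within-country only: without → with country | 1.3 is the total: without → with country |
|---|---|---|
| 1.0 | 87% → 87% | 87% → 87% |
| 1.25 | 85% → 87% | 88% → 90% |
| 1.35 | 83% → 87% | 89% → 92% |
| 1.5 | 79–80% → 87% | exceeds 1.3 |
| 2.0 | 64% → 86% | exceeds 1.3 |

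**5. Direction of the error (1.3 within-country only).** At r = 2 under the 40% effect, the mean estimated SE without country is 0.099 per 100 PY, against a true SD of 0.070; with country it is 0.070. One-sided type I error without country is 5% at r = 1, 4% at 1.25, 2.5% at 1.5 and 0.7% at 2.0. With country it stays at about 5%.

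**6. Pairs kept (same reading of 1.3).** A within-country paired test on 7 df, with matching assumed to add nothing beyond country, has power of about 84% at ratios 1.0 to 1.5 and 82% at 2.0. Its mean SE at r = 2 is 0.071, so pairing already removes the country component.

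**The case against.** - **Pairing may already deal with it.** Sections 6 and 15.5 say Phase B is pair-matched. Pairs formed within country and kept in Stage II remove the country difference without a covariate. This stands. A reader might infer that Phase B breaks its pairs because the VHT SAP does, or because 15.5 uses leave-one-out selection. Neither shows it: the VHT statement governs that trial, and 15.5 does not say whether a community or a pair is left out. Section 15 is an overview and the supplied SAPs cover Phase A only, so a Phase B SAP may settle the matter.
- **The large losses sit outside the plan's own variance.** A reader might take 64% as the expected power. It needs a two-fold country ratio on top of a within-country design effect of 1.3, a total of 2.77. The documents support neither. If 1.3 is the total, power without country does not fall below its value with no country difference, and country adds at most about 3 points. This stands, so both readings are shown.
- **Listed covariates may absorb country.** Baseline prevalence or suppression could do so in part. That depends on usable ministry records in control communities, which are not assured.
- **The VHT comparison is imperfect.** That trial breaks its matches, targets an individual-level effect, and offers country as a candidate without forcing it. It shows the team's practice, not a rule for Phase B.
- **The error is conservative.** This is correct, and it limits the severity.

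**Conclusion.** The omission is real: country is a randomisation stratum and is not on the closed Stage II list. Its consequence is conditional on pairs being broken or never formed and on no selected covariate tracking country. The documents settle neither condition, so they do not support saying that country differences will remain in the error term. Nor do they support a reading of bias or inflated type I error, because stratification balances country across arms.

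The gain from including country ranges from little or nothing (pairs kept), through 2 to 3 points of one-sided power at ratios 1.25 to 1.35 (1.3 as the total), to about 4, 7 and 22 points at 1.35, 1.5 and 2.0 (1.3 within-country only). All the ratios are assumptions. The change is worth making because it is cheap, follows the randomisation and matches the team's Phase A practice.

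**What to change.** Before Phase B outcomes are unblinded:

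1. In 15.5, state whether Stage II keeps the matched pairs and whether leave-one-out means a community or a pair.
2. Reconcile the lottery in 9.1.2 with the pair-matching in sections 6 and 15.5.
3. If pairs are broken or were not formed, include country in the Stage II adjustment for HIV incidence, and carry it to the secondary outcomes that use the analogous approach. State the reference distribution and reduce its degrees of freedom by one for the country term (14 to 13 in the unpaired comparison above).
4. Keep the secondary unadjusted contrast of arm means as defined. If pairs are kept, no country term is needed.

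The cost is a few sentences and one degree of freedom. If the countries do not differ, the simulated power loss is about 0.2 points (87.6% to 87.4%), and at most about 0.4.
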